### 8.3.2 Part 2 - AGI-134 at the RP2D

Safety interim analyses are planned after 3 subjects with deep injectable lesions have completed the first cycle with AGI-134 (i.e. Cycle 1 - Day 1 through to Cycle - Day 21). Sites will be required to contact the Sponsor within 24 hrs if a subject present with a DLT during the DLT assessment period (see Section 3.1.1).

During Part 2, 3 subjects will be evaluated after one cycle of injection into deep lesions. If one or more of the subjects experiences DLTs, a new assessment will be done after the additional 3 subjects with deep lesions injected are enrolled and treated (total 6 subjects). If no new DLTs are reported, the recruitment will continue as planned. If 2 or more subjects presented a DLT, the SC will assess the risk vs. benefit of the treatment and recommend whether or not the dose of AGI-134 should be reduced and/or the treatment schedule be changed (see Section 8.3).

Following the assessment of the first 3 patients with deep lesion injected or 6 patients if expansion is needed, the safety data will be evaluated by the Safety Committee. Evaluation by

agalin A subsidiary of Bio	nnune DLINERX	PRIVILEGED & CONFIDENTIAL
Investigational Product: AGI-134		Protocol No. AGI-134.FIM.101
Phase: I/IIa		Version 6.1 31 May 2021

the Safety Committee will be conducted every 6 months to review ongoing safety data, until the last patient last visit (LPLV).

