	During the first cycle of treatment for each dose, a subject that experiences a dose-limiting toxicity (DLT) or an adverse event (AE) of moderate or high severity, assessed as related to AGI-134 and as clinically significant, will trigger an expansion of the dose level group to a total of three subjects, and the study will continue in a conventional "3+3" design. If the AE is a DLT, an expansion of the dose level to a total of 6 subjects prior to escalation to the next dose level will be triggered and will be performed in a stepwise manner, dosing an additional two subjects in the first dose expansion step, followed by an additional three subjects that would be dosed only if no second DLT occurs.

20		PRIVILEGED & CONFIDENTIAL
Investigational Product: AGI-134		Protocol No. AGI-134.FIM.101
Phase: I/IIa		Version 6.1 31 May 2021

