#### Part 2:

- a) After 3 subjects with deep injectable lesions (or 6 subjects, if expansion is needed) have completed the first cycle of treatment with AGI-134 (i.e. Cycle 1/Day 1 through to Day 21).
- b) Every 6 months to review ongoing safety data until the last patient last visit (LPLV).

During this part, 3 subjects will be evaluated after one cycle of injection into a deep lesion. If one or more of the subjects' experiences DLTs, a new assessment will be done after additional 3 subjects with deep lesions injected are enrolled and treated (total of 6 subjects). If no new DLTs are reported, the recruitment will continue as planned. If 2 or more subjects presented a DLT, the Safety Committee will assess the risk vs. benefit of the treatment and recommend whether or not the dose of AGI-134 should be reduced and/or the treatment schedule be changed (see Section 8.3: Ongoing Safety Assessment and Dose-Limiting Toxicity).

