### 8.3.1 Part 1 – Accelerated Dose Escalation of AGI-134

At any given dose, if one subject presents with a dose-limiting toxicity (DLT) or an event of moderate or higher severity assessed as related to AGI-134 and as clinically significant during the first cycle of treatment, the group of subjects will be expanded and the study will continue in a conventional "3+3" design. The expansion after an event of moderate severity will be to a total of 3 subjects and the expansion after a DLT will be to a total of 6 subjects, recruited in a stepwise manner of 3+3. Moderate injection site reactions are expected events with any injectable drug, as are moderate drug administration-related fever, nausea and vomiting. These will therefore will not be considered as a trigger for conversion to a "3+3" design. If the group of subjects was expanded due to a clinically significant related event that is not a DLT, and this expanded group, i.e. 3 subjects, showed no DLT events, then the study will continue to the next dose level enrolling 3 subjects.

If 1 out of 3 subjects presented with a DLT in the expanded cohort, a group of additional 3 subjects will be treated at the same dose level. If no more DLTs are reported at that dose, i.e. only 1 out of a total of 6 subjects has developed a DLT, the dose escalation will continue to the next level. At any given dose, if 2 or more out of 6 subjects experience a DLT, that dose level will be considered as the DLT dose. In such a case, 3 more subjects will be administered at the previous dose level, if there are less than 6 subjects already treated at that dose. MTD is defined as the highest dose level in which 6 subjects have been administered with and less than 2 instances of DLT.

When the first subject in each dose completes the first cycle of treatment, (each Cycle is 3 weeks long), the safety and tolerability will be assessed by a Safety Committee to decide whether to escalate the dose or to expand the group of subjects. When the MTD is reached or the 200 mg dose is found to be safe, whichever comes first, it will be defined as the RP2D and the study will continue to Part 2.

After completion of the first treatment cycle, subjects in Part 1 of the study will continue receiving intratumoural injection at the dose determined at Screening for 3 additional cycles. No intra-subject escalation will be allowed. The treatment regimen is one dose per cycle of AGI-134 every three weeks for up to 4 cycles.

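### The Part 2 deep-lesion run-in text permits three more doses after DLTs in 2 or 3 of the first 3 subjects, and Section 3.1.1 gives a DLT window only to those first 3

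*Combined protocol and SAP*

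**What the plan says.** **Run-in.** The Synopsis and Sections 3.1, 8.3.2 and 9.7 give the same Part 2 rule. Section 8.3.2 states "Safety interim analyses are planned after 3 subjects with deep injectable lesions have completed the first cycle with AGI-134", and then "If one or more of the subjects experiences DLTs, a new assessment will be done after the additional 3 subjects with deep lesions injected" have been enrolled and treated, making six. It goes on: "If no new DLTs are reported, the recruitment will continue as planned". And: "If 2 or more subjects presented a DLT, the SC will assess the risk vs. benefit of the treatment", followed by a recommendation on whether to lower the dose or change the schedule. On timing, Section 3.1 puts the interim analysis as "After 3 subjects with deep injectable lesions (or 6 subjects, if expansion is needed) have completed the first cycle of treatment with AGI-134". Section 8.3.2 closes in the same way: after the first 3, "or 6 patients if expansion is needed, the safety data will be evaluated by the Safety Committee".

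**Part 1, for comparison.** Section 8.3.1: "If 1 out of 3 subjects presented with a DLT in the expanded cohort, a group of additional 3 subjects will be treated" at that dose. The Synopsis describes the stepwise expansion after a DLT as two more subjects, "followed by an additional three subjects that would be dosed only if no second DLT occurs".

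**DLT window.** The Synopsis sets Cycle 1 Day 1 to Day 21 for both parts, with no limit on who is covered. Section 3.1.1 gives the same days for Part 2 but confines them to the first three deep-lesion subjects. Section 8.3 defines the period for the accelerated escalation only. Section 8.3.3 requires a DLT to fall within the period defined in Section 3.1.1.

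**Accrual stop.** Sections 3.1.1 and 8.3 stop Part 2 accrual when a specific AE meeting the DLT definition exceeds 30%. Neither gives a minimum number of subjects.

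**The concern.** A run-in of three should protect the next three. Here one instruction covers one, two or three DLTs in three, and that instruction is to treat three more and then reassess. The Committee sentence is tied to neither three nor six subjects and is not written as a condition for the next dose. In a first-in-human study whose Part 1 is limited to superficial, palpable tumours, Part 2 thus has the looser written rule for the less familiar route.

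The window wording weakens the same decision from the other side. The expansion is judged on new DLTs in subjects 4 to 6, yet under Section 3.1.1 those subjects have no DLT window. Superficial-lesion subjects have none either, although the >30% stop is meant to watch all of Part 2. What is at stake is exposure of up to three further subjects, and DLTs that go uncounted. No sample size, power or efficacy analysis is affected.

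**Working it through.** The plan gives no operating characteristics for the Part 2 rules, so there is no figure to reproduce. Inputs from the documents: 3 subjects, then 3 more; thresholds of 1 or more and 2 or more; the 30% limit; about 35 Part 2 subjects. The true DLT rate p is not given; I take 10% to 50% and treat subjects as independent.

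**Step 1: reading the run-in by outcome.**
- 0/3: recruitment continues.
- 1/3: three more are treated. No new DLT means continue; one or more new DLTs makes at least 2 in 6, and the Committee assesses.
- 2/3 or 3/3: the expansion sentence applies as written. The Committee sentence also applies, with no order between them and no hold.
- 2/3 or 3/3, then 0/3: the instruction to continue and the instruction to assess both apply.

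**Step 2: how often this matters.**
- P(1 or more of 3) = 1 − (1−p)³
- P(2 or more of 3) = 3p²(1−p) + p³
- P(2 or more of 3, then 0 of 3) = P(2 or more of 3) × (1−p)³

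| p | P(1 or more of 3) | P(2 or more of 3) | Share of expansions starting from 2/3 or 3/3 | Both instructions apply |
|---|---|---|---|---|
| 10% | 27.1% | 2.8% | 10% | 2.0% |
| 20% | 48.8% | 10.4% | 21% | 5.3% |
| 30% | 65.7% | 21.6% | 33% | 7.4% |
| 40% | 78.4% | 35.2% | 45% | 7.6% |
| 50% | 87.5% | 50.0% | 57% | 6.3% |

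Example at p = 20%: 3 × 0.04 × 0.8 + 0.008 = 0.104; 1 − 0.512 = 0.488; 0.104/0.488 = 21%; 0.104 × 0.512 = 5.3%. If three more are dosed, the chance of at least one further DLT equals the second column.

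**Step 3: the window.** Section 8.3.3 requires the event to fall in the Section 3.1.1 period. Section 3.1.1 supplies a Part 2 period for three subjects only. Put together, subjects 4 to 6 cannot produce the new DLTs that decide the run-in, and the 24-hour DLT report in Section 8.3.2, which refers to the same period, does not cover them. The Synopsis gives the opposite result.

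**Step 4: the >30% stop.** The smallest count above 30% is 1 of 3 (33%), 2 of 6 (33%), 4 of 10 and 11 of 35. If the stop is applied to the first 3 subjects, one DLT halts accrual while the run-in says to enrol three more. If one specific AE has true rate p and is checked after every subject up to 35 (exact recursion), the chance of stopping is:

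| p | from n = 1 | from n = 6 | from n = 10 |
|---|---|---|---|
| 10% | 30.3% | 13.4% | 4.0% |
| 40% | 98.1% | 97.3% | 96.2% |

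The unstated minimum therefore matters most when the AE is uncommon.

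**The case against.** The strongest reply is that the Committee sentence already covers 2/3. An analysis is planned at three subjects, that sentence is not tied to six, and the clause about no new DLTs fits the 1/3 branch. On this reading the Committee intervenes at 2/3 and the double instruction never arises. There are other safeguards: DLT reports within 24 hours, SAE reports within 24 hours whatever the DLT window, sponsor safety staff on the Committee, review every six months, and a termination clause for unacceptable risk. This stands as far as it goes. A reader might infer that the plan requires three more doses after 2/3, or that nobody looks at three subjects. The documents support neither. But no safeguard is written as a hold on the next deep-lesion dose, and the timing text moves the evaluation to six when expansion is called for, which it is at 2/3 too.

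On the window, the intended meaning can be inferred from the Synopsis and from a run-in that assesses six. That is fair, but the section that Section 8.3.3 cites is the narrow one.

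On the stop, a reader might infer a definite clash with the run-in. The rule speaks of Part 2 generally, so treated Part 2 subjects are the natural denominator, and no text makes the deep run-in the denominator. The clash is conditional. The missing minimum is real, although a stop followed by review is precautionary and reversible.

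Finally, the Part 2 dose will be the MTD or a 200 mg dose found safe, and is capped by tumour dimensions, so low DLT rates are plausible. At 10% the run-in gap is reached in only 2.8% of trials. Higher rates cannot be excluded for deep injection, which Part 1 does not test.

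**Conclusion.** The point holds as a safety-relevant wording defect that should be fixed. The literal run-in text permits, without requiring, three more deep-lesion doses after 2/3 or 3/3, and nothing holds dosing until the Committee has reviewed. That state is reached with probability 2.8% at a 10% DLT rate and 50% at 50%. These are chances that the gap comes into play, not chances that three more subjects are dosed, because the Committee may act at three. They rest on assumed DLT rates and independence between subjects.

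The conflict between Section 3.1.1 and the Synopsis needs no probability: read literally, it removes subjects 4 to 6 and all superficial-lesion subjects from DLT assessment. The absent minimum for the >30% stop is secondary.

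**What to change.** 1. In the Synopsis and Sections 3.1, 8.3.2 and 9.7, use one rule. At 0/3, continue. At exactly 1/3, add three and continue if no more than 1 of 6 has a DLT. Once 2 or more of the first 6 deep-lesion subjects have had a DLT, dose no new deep-lesion subject until the Safety Committee has reviewed. What the Committee may recommend is unchanged.
2. In Sections 3.1.1 and 8.3, give every Part 2 subject the Cycle 1 Day 1 to 21 DLT window, as in the Synopsis.
3. State that the >30% stop is calculated over DLT-evaluable Part 2 subjects from a stated minimum, for example 6, with the run-in rule governing deep-lesion dosing before that. One DLT in 3 then leads only to expansion.

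**Cost.** Protocol wording only. No subjects or visits are added, because the Part 2 schedule already has Cycle 1 safety visits for everyone. The run-in change mainly brings the review forward. It adds a pause only when subjects 4 to 6 have 2 or more DLTs after 0/3. Under the present text, the run-in reaches two DLTs with probability P(2 or more of 3) + 3p(1−p)² × [1 − (1−p)³], which is 9.4% at p = 10% and 29.1% at 20%. Under the fix it is P(2 or more of 6), 11.4% and 34.5%. The difference is about 2 and 5 percentage points. Below the stated minimum, superficial-lesion DLTs would rest on 24-hour reporting and ongoing review.

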# Ongoing Safety Assessment and Dose-Limiting Toxicity

AEs will be reported from the time of informed consent signature Up to 30 days after the last dose of study drug or until the initiation of new anticancer treatment, whichever is sooner. SAEs will be reported until 90 days after the last dose of study drug, or until the initiation of new anticancer treatment, whichever is sooner.

agalin A subsidiary of Bit	OLINERX	PRIVILEGED & CONFIDENTIAL
Investigational Product: AGI-134		Protocol No. AGI-134.FIM.101
Phase: I/IIa	doses of AGI-134 in unresectable/metastatic solid tumours.	Version 6.1 31 May 2021

Study Assessments	The period considered for DLT assessment is defined for Part 1 and Part 2, as the time from the first dose administration of AGI-134 and up to the end of the first cycle of therapy (e.g., Cycle 1/Day 1 through to Cycle 1/Day 21).  After the DLT assessment period, data will be assessed an ongoing manner during the study. All AEs should be captured within the eCRF; AEs reported beyond the DLT period will not be considered for the DLT assessment.
	General instructions before study drug administration
	The following instructions should be followed before AGI-134 administration:
	
 
AGI-134 should only be administered when personnel and therapies are immediately available for the treatment of hypersensitivity reactions, should they occur. This should include having an open IV cannula and fluid therapy readily available.
 

	
 
Hypovolaemia, if present, should be corrected prior to administration of AGI 134 according to the study site standard of care.
 

	
 
For patients who receive routine anti-hypertensive medication, these medications should be withheld in the 24 hours prior to injection of AGI-134.
 

	Recommendations for patients who experience systemic reactions related to study drug are detailed in section 5.7.
Study	The duration of core study participation is 54 weeks.
Duration	A Termination visit will be performed for all subjects on Week 54. Long-term follow-up will continue for all subjects for up to 5 years.
	The study consists of the following study periods:
	Screening Period: up to 28 days
	Core Study: up to 54 weeks
	Long-Term Follow-Up: Following Termination/Early Termination visit, a follow-up telephone call will be performed to all subjects every 9 weeks up to 5 years in order to assess duration of response and survival.
Planned	Part 1: Up to 24 subjects.

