### 3.1.1 Ongoing Safety Assessment and Dose-Limiting Toxicity

AEs will be reported from the time of informed consent signature up to 30 days after the last dose of study drug or until the initiation of new anti-cancer treatment, whichever is sooner. SAEs will be reported until 90 days after the last dose of study drug, or until the initiation of new anti-cancer treatment, whichever is sooner. The period considered for DLT assessment for Part 1 is defined as the time from the first dose administration of AGI-134 and up to the end of the first cycle of therapy (i.e. Cycle 1/Day 1 to Cycle 1/Day 21).

agalin A subsidiary of BIG	PRIVILEGED & CONFIDENTIAL
Investigational Product: AGI-134	Protocol No. AGI-134.FIM.101
Phase: I/IIa	Version 6.1 31 May 2021

The period considered for DLT assessment for Part 2 is defined as the time from the first dose administration of AGI-134 and up to the end of the first cycle of therapy (i.e. Cycle 1/Day 1 to Cycle 1/Day 21) for the first 3 subjects with deep lesions.

After the DLT assessment period, data will be assessed on an ongoing basis during the study. All AEs should be captured within the eCRF, however AEs reported beyond the DLT period will not be considered for the DLT assessment.

During Part 2 of the study, any specific AE that fits the DLT definition and occurs at a frequency of > 30% will stop accrual. In this scenario, the Safety Committee may recommend a lower dose level or dosing schedule change for the continuation of the expanded cohort. The study will be discontinued or terminated in case of an unacceptable risk or a negative change in the risk/benefit assessment. This might include the occurrence of adverse events for which character, severity or frequency is unexpected and overcome the potential benefit of the study drug. In addition, any data deriving from other clinical trials or toxicological studies which negatively influence the risk/benefit assessment might cause discontinuation or termination of the study.

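### The protocol gives two different timings for the six-subject deep-lesion DLT review in Part 2

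*Combined protocol and SAP*

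**What the plan says.** Part 2 reviews safety after the first 3 subjects injected in deep lesions. If any of them has a DLT, 3 more are added and a new assessment follows.

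- **Timing in item (a), Synopsis and Section 3.1:** "After 3 subjects with deep injectable lesions (or 6 subjects, if expansion is needed) have completed the first cycle of treatment with AGI-134", with the cycle spelled out as Day 1 through Day 21. This covers both the three-subject and the six-subject review.
- **Timing in the decision paragraph:** Section 8.3.2 places the new assessment after "the additional 3 subjects with deep lesions injected are enrolled and treated (total 6 subjects". The Synopsis and Section 9.7 word it the same way. Section 3.1 has "additional 3 subjects with deep lesions injected are enrolled and treated (total of 6 subjects", directly below its own item (a).
- **Consequence of that assessment:** "If no new DLTs are reported, the recruitment will continue as planned".
- **Lead sentence of Section 8.3.2:** "Safety interim analyses are planned after 3 subjects with deep injectable lesions have completed the first cycle with AGI-134". Item (a)'s clause about six subjects is missing here.
- **DLT period, Synopsis:** "The period considered for DLT assessment is defined for Part 1 and Part 2, as the time from the first dose administration of AGI-134", running to the end of Cycle 1, with no limit on which Part 2 subjects it covers.
- **DLT period for Part 2, Section 3.1.1:** "i.e. Cycle 1/Day 1 to Cycle 1/Day 21) for the first 3 subjects with deep lesions".

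**The concern.** A DLT is defined over a 21-day window, so a finding of no new DLTs means something only once each added subject has been observed through that window. The first 3 subjects are reviewed after a full cycle. For the added 3, the decision paragraph asks only that they have been recruited and dosed, which can be true on the day the last of them receives AGI-134.

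This review takes place only after a DLT has been seen, in a first-in-human study. It also concerns deep lesions, whereas Part 1 enrolled subjects with superficial, palpable tumours. If the review were held on incomplete windows, late-onset events in the added subjects would be missing from the decision to carry on recruiting.

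**Working it through.** The documents state no error rate or operating characteristic for this review, so there is no plan figure to reproduce. The check is a comparison of the text, followed by an illustration of scale.

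**Step 1. Set the sections side by side.**

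| Place | First 3 subjects | Six subjects | DLT period for the added 3 |
|---|---|---|---|
| Synopsis | Cycle 1 complete | Item (a): Cycle 1 complete. Decision paragraph: added 3 dosed | Day 1 to Day 21, no subject limit |
| Sections 3.1 and 3.1.1 | Cycle 1 complete | Item (a): Cycle 1 complete. Decision paragraph: added 3 dosed | Worded for the first 3 only |
| Section 8.3.2 | Cycle 1 complete | Added 3 dosed | Refers to 3.1.1 |
| Section 9.7 | After one cycle | Added 3 dosed | Not stated |

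**Step 2. Confirm that it is one review.** Item (a)'s six subjects exist only if the group is expanded, and the decision paragraph's total of six is that same expanded group. The two timings therefore apply to the same decision.

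**Step 3. See which sections correct themselves.** In the Synopsis and Section 3.1 the reader sees both timings. In 8.3.2 and 9.7 only the dosed wording applies to the six. Section 8.3.2 adds that the Safety Committee evaluates the data following the assessment of 3 or 6 patients, but does not say when that assessment falls.

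**Step 4. Follow the cross-reference.** Section 8.3.2 and the DLT definition in 8.3.3 both point to 3.1.1 for the assessment period. For Part 2, 3.1.1 confines that period to the first 3 deep-lesion subjects. The general text of Section 8.3 defines it for the accelerated escalation only. Someone working from Section 8 is thus led to a definition that does not cover the added 3.

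**Step 5. Compare Part 1.** Item (c) for Part 1 in Section 3.1 requires six subjects to have completed the first cycle. The protocol does state completion explicitly elsewhere.

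**Step 6. Scale, for illustration only.** Suppose the review fell on the day the third added subject was dosed, with dosing s days apart. The added subjects would then have 2s, s and 0 days of follow-up. The number with less than 21 days would be:

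- s = 0 or 7: 3 of 6 (50%)
- s = 14 (28, 14 and 0 days): 2 of 6 (33%)
- s = 21 (42, 21 and 0 days): 1 of 6 (17%)

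Now let p be the true DLT risk per subject and f the share of DLTs already visible at the review, taken as equal for the three added subjects. Both are assumptions. The chance of seeing no new DLT is (1 − f·p)³.

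| p | f = 1 (full window) | f = 0.75 | f = 0.5 | f = 0.25 |
|---|---|---|---|---|
| 0.1 | 0.729 | 0.791 | 0.857 | 0.927 |
| 0.2 | 0.512 | 0.614 | 0.729 | 0.857 |
| 0.3 | 0.343 | 0.465 | 0.614 | 0.791 |
| 0.4 | 0.216 | 0.343 | 0.512 | 0.729 |

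For example, at p = 0.3 and f = 0.5, (1 − 0.15)³ = 0.614, against (1 − 0.3)³ = 0.343 with complete windows, a difference of 0.271. Under item (a), f = 1 and the difference is zero.

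**The case against.** The strongest reply is that item (a) already settles the matter. It names the six-subject review and requires a completed cycle. On that view the dosed wording only says who is added. It says after, not on the day of. It also follows a sentence in which the first 3 are evaluated after one cycle, so a new assessment is naturally the same kind of assessment repeated. Part 1 uses similar shorthand: Section 8.3.1 speaks of 3 more subjects being treated, while Section 3.1 sets the review after cycle completion.

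Much of this stands. A reader might infer that the protocol lets recruitment be cleared before Day 21, or that subjects still inside their window are counted as free of DLTs. The documents support neither. No section says that the review may be held early or that incomplete windows count. Section 4.5 provides for replacing subjects withdrawn before completing the DLT period, which points the other way, although it deals with withdrawals and not with subjects still in follow-up.

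There are also backstops. Section 8.3.2 requires DLTs to be reported to the Sponsor within 24 hours. Sections 3.1.1 and 8.3 stop Part 2 accrual if a specific DLT-type event exceeds 30%. Safety is monitored throughout. These are partial: none fixes the date of this review, and the 24-hour rule in 8.3.2 uses the same 3.1.1 period that is worded for the first 3.

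The reply does not fully answer the point. The dosed wording is introduced as a statement of when the assessment is done, and the sections on DLT assessment and on the Safety Committee do not repeat item (a)'s rule for six.

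**Conclusion.** The protocol is inconsistent on when the six-subject deep-lesion review takes place and on whether the 21-day Part 2 DLT period covers the added 3 subjects. Early judgement of no new DLTs is open on one reading of 8.3.2 and 9.7 taken alone. The Synopsis and Section 3.1 also contain the rule that would prevent it.

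No single probability of wrongly continuing recruitment should be attached to this. It is zero if item (a) is followed. Otherwise it depends on accrual spacing, DLT risk, DLT onset and the interval between last dosing and review, none of which the documents give. The figures in the working show only that timing could matter. Severity is minor to moderate: the text affects a continue-or-not safety decision taken after a DLT signal, but the protocol already holds wording that resolves it.

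**What to change.** Reconcile the passages at the next amendment.

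1. In the decision paragraph of the Synopsis and Sections 3.1, 8.3.2 and 9.7, use for the six subjects the trigger that item (a) already states: completion of Cycle 1, Day 1 through Day 21.
2. In the lead sentence of Section 8.3.2, carry over item (a)'s clause for six subjects if expanded.
3. Align the Part 2 DLT-period wording in Section 3.1.1 with the Synopsis, so that it is not confined to the first 3 deep-lesion subjects.

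The cost is one phrase in four places plus two short alignments. The six-subject review may come up to three weeks after the last added subject is dosed, a wait that item (a) already implies.
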